- b. Serum β -hCG pregnancy testing is to be performed for female subjects of childbearing potential during Screening, and a urine pregnancy test is to be performed within 24 hours before the first dose on Day 1 (Baseline). Subjects with a positive serum pregnancy test result are not eligible for study participation. Serum pregnancy testing is to be repeated at the Week 56 Follow-up visit or at Early Termination (whichever takes place sooner), and during the study any time pregnancy is suspected. Female subjects of childbearing potential are required to perform urine home pregnancy tests monthly between study visits and the results should be recorded in a subject diary. A positive urine test should be followed by an unscheduled serum pregnancy test as soon as possible. Study drug is to be held in the event of a positive urine pregnancy test and permanently discontinued for any subject with a positive serum pregnancy test result.
- c. A complete medical history is to be documented during Screening and updated at Baseline, prior to administration of the first study drug dose. A history of harmful alcohol intake for a period of more than 3 consecutive months within 1 year prior to Screening in the judgement of the Investigator is exclusionary.

- d. Active substance abuse, including inhaled or injected substances (cocaine and other illegal/banned substances; any opiate, amphetamine, or benzodiazepine for which the subject does not have an existing prescription), within 1 year prior to Screening is exclusionary. However, recreational cannabis/tetrahydrocannabinol use is permissible.
- e. To qualify for this study, liver histology results must be available before randomization (randomization is within 3 days of Baseline [Day 1]). If the subject terminates early from the study, the end of study biopsy is only required if the subject has completed at least 42 weeks of treatment. See Section 8.1, Criterion 7, and Section 8.2, Criterion 20 for detailed requirements for histology results.

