- m. Baseline eye examinations may be performed at any time during the Screening period. Eye exams at Week 4, Week 8, Week 13, Week 26, Week 39, Week 52, Week 56 and/or Early Termination are required only if eye-related signs or symptoms are reported by the subject or observed by the investigator. If a subject experiences a treatment-emergent eye abnormality, an eye examination inclusive of slit lamp and near and far visual acuity testing should be performed by a qualified ophthalmologist or optometrist within 24 to 48 hours of event onset or on the next business day after symptom onset to evaluate the abnormality.
- n. Hematology and coagulation parameters include hemoglobin, MCV, MCHC, hematocrit, platelet count, RBC count, WBC count with differential, ANC, and PT, aPTT, INR, and fibrinogen. See also [Table 5](#).
- o. Liver aminotransferases include AST and ALT. Liver aminotransferases collected as part of the clinical chemistry panel for safety are also applicable for efficacy assessments.
- p. Fasting clinical chemistries include chloride, carbon dioxide, sodium, potassium, glucose, BUN, calcium, magnesium, creatinine, albumin, ALT, AST, ALP, GGT, total bilirubin, indirect and direct bilirubin, and total protein. CPK (total and fractionated) is to be reported at Screening and at Baseline. See also [Table 5](#).
- q. Urinalysis includes specific gravity, pH, blood, glucose, protein, ketones, and microscopic examination of sediment, if present. See also [Table 5](#).
- r. Subject contact to reliably assess medication use between visits is encouraged around Week 10, Week 17, Week 23, Week 30, Week 34, Week 43, and Week 47. See Section 9.7 for a list of accepted and excluded concomitant medications. If a subject receives a vaccine, including the COVID-19 vaccine, details regarding that vaccine should be recorded as a concomitant medication(s), including manufacturer, dose, and dates of each injection. Any vaccine-related reactions should be recorded as described in Section 12.2.
- s. The same biopsy samples will be used for histology analysis by the central study pathologist and by digital pathology.

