In the event a subject is unable to complete the end of treatment MRI-PDFF and/or liver biopsy within the protocol-specified window (Week 52 \pm one week), extended dosing is permitted to maintain continuous dosing up to the time both assessments are completed, to a maximum total of 56 weeks of dosing. In this instance, the Follow-up visit at Week 56 for post treatment safety and efficacy assessments is to be adjusted to occur four weeks after the last dose (\pm one week).

In the instance of a dose hold due to an AE or SAE, the decision to resume study drug will require consultation with the Investigator, the CRO’s Medical Monitor, and the Sponsor’s Chief Medical Officer.

Improvement of NAS and improvement of fibrosis score will be evaluated by comparison of Baseline and Week 52 liver histology specimens. Subjects will also undergo MRI-PDFF prior to the start of treatment, at Week 26, and at Week 52 or Early Termination unless it presents a logistical or physical hardship to the subject. MRI-PDFF is not required at Early Termination if a

subject has completed less than 22 weeks of study treatment. Other efficacy and PD assessments include FibroScan with CAP, and measurement of liver aminotransferases, lipid parameters, and other noninvasive biomarkers of NASH and liver fibrosis throughout the study.

During the study, safety will be assessed by vital signs, 12-lead ECGs, physical examinations including eye examinations, and clinical laboratory testing. Subjects will be evaluated for AEs and concomitant medication use throughout the study.

[REDACTED]

[REDACTED].

An independent data monitoring committee (IDMC) will be established by charter to provide independent review and assessment of study data and to monitor the overall study conduct in a systematic manner to safeguard the safety of study subjects. The IDMC will be tasked with making recommendations to the Sponsor to continue, amend, or stop the study based on these assessments.

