steatohepatitis is defined as absent fatty liver disease or isolated or simple steatosis without steatohepatitis and a NAS score of 0-1 for inflammation, 0 for ballooning, and any value for steatosis.

AND

- Improvement in liver fibrosis greater than or equal to one stage (NASH CRN fibrosis score) and no worsening of steatohepatitis (defined as no increase in NAS for ballooning, inflammation, or steatosis).
- Proportion of subjects experiencing **both** of the following at Week 52:
 - Histological improvement at Week 52 in nonalcoholic fatty liver disease (NAFLD) activity score (NAS) (i.e., ≥ 2 points improvement in NAS with ≥ 1 point improvement in ballooning or inflammation) and without worsening of fibrosis (by NASH Clinical Research Network [CRN] fibrosis score)

AND

- Improvement in liver fibrosis greater than or equal to one stage (NASH CRN fibrosis score) and no worsening of steatohepatitis (defined as no increase in NAS for ballooning, inflammation, or steatosis).
- Proportion of subjects with resolution of steatohepatitis and no worsening of liver fibrosis (by NASH CRN fibrosis score). Resolution of steatohepatitis is defined as absence of fatty liver disease or isolated or simple steatosis without steatohepatitis and a NAS of 0 or 1 for inflammation, 0 for ballooning, and any value for steatosis at Week 52.
- Proportion of subjects with histological improvement (decrease) at Week 52 in NAS by ≥ 1 point.
- Proportion of subjects with histological improvement (decrease) at Week 52 in NAS by ≥ 2 points.
- Change and percent change from Baseline in MRI-PDFF liver fat (%) at Week 26.
- Change and percent change from Baseline in MRI-PDFF liver fat (%) at Week 52.
- Proportion of subjects with NASH resolution (defined as absence of fatty liver disease or isolated or simple steatosis without steatohepatitis and a NAS of 0 or 1 for inflammation, 0 for ballooning, and any value for steatosis) at 52 weeks.
- Change from Baseline in ALT, AST, alkaline phosphatase (ALP), and GGT at Weeks 26 and 52 and at each study visit.
- Change from Baseline in LDL-C and other lipid levels (including LDL/HDL ratio) at Weeks 26 and 52 and at each study visit.
- Change from Baseline in collagen/fibrous area and fibrosis score, assessed by digital pathology, at Week 52.
 - The primary digital pathology variables that will be analyzed include the following:
 - qFibrosis – continuous value

- qFibrosis – stage
- qSteatosis – continuous value
- qSteatosis – grade

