9.2. Secondary Efficacy Endpoints and Analyses

Secondary efficacy analyses for the other histological responder endpoints will be analyzed in the ITT and mITT populations using the methods described for the primary efficacy endpoint.

Secondary efficacy analyses of endpoints expressed as percent change or change from Baseline only at Week 26 or only at Week 52 will be analyzed in the ITT analysis set using an analysis of covariance (ANCOVA) model with fixed effects for T2DM status at baseline (Yes, No) and treatment group, and a covariate term for baseline analysis value of response. Least squares (LS) means for the percent change from Baseline by treatment and the associated standard errors, the

LS means for the difference between treatment groups, and the associated two-sided 95% CIs and two-sided p-values, based on t-tests, will be derived from the ANCOVA model.

For secondary endpoints assessed at multiple visits, a linear mixed-effects model for repeated measures (MMRM) may be used. The model will include T2DM status at baseline (Yes, No), treatment group, visit, and treatment-by-visit interaction as the fixed effects, and baseline value as a covariate, and the model will use an unstructured variance-covariance matrix. The point estimates for the least-squares mean of the difference treatment groups at each visit and the corresponding 95% confidence interval and two-sided p-value will be summarized. If convergence problems arise when fitting the model, a spatial power covariance structure will be used as a first step. If the model still has convergence issues, compound symmetry covariance structure will be employed. The Kenward-Roger correction for the denominator degrees of freedom will be applied.

ALT, AST, ALP, and GGT will also be summarized in shift tables of baseline to each visit based on range categories of low (below lower limit of normal [LLN], normal, and high [above upper limit of normal [ULN]]).

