The continuous digital pathology variables (qFibrosis, qSteatosis, and Steatosis corrected qFibrosis) will be summarized descriptively with change from baseline being analyzed using MMRM methods. Digital pathology stage/grade variables (qFibrosis – stage, qSteatosis – grade, and Steatosis corrected qFibrosis – stage) will be summarized descriptively with change from baseline being analyzed using ANCOVA methods. The ANCOVA models will include fixed effects for treatment group, T2DM status at baseline (Yes, No), and amount of fibrosis at baseline (F2 or F3), and baseline value as a covariate. Shifts in stage from baseline to each visit will also be presented. The shifts will include decrease in stage, no change in stage, and increase in stage. The shifts will be compared between treatment groups using a CMH-row mean scores test.

Graphical display for selected secondary endpoints will be provided.

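### SAP 9.2 assigns a repeated-measures model to digital-pathology variables that have one post-baseline value, leaves F2/F3 out of that model, and names no strata for the stage-shift test

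*SAP*

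**What the plan says.** **Data.** Digital pathology has no sampling of its own. Protocol Table 2, footnote s: "The same biopsy samples will be used for histology analysis by the central study pathologist and by digital pathology". Protocol 7.1 says that histological change is "evaluated by comparison of Baseline and Week 52 liver histology specimens". After early termination, footnote e of the same table says "the end of study biopsy is only required if the subject has completed at least 42 weeks of treatment". SAP 5.1 defines the endpoint at one time: "Change from Baseline in collagen/fibrous area and fibrosis score, assessed by digital pathology, at Week 52".

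**General model rule.** SAP 9.2 sends "Secondary efficacy analyses of endpoints expressed as percent change or change from Baseline only at Week 26 or only at Week 52" to ANCOVA, with T2DM, treatment and baseline value. It allows an MMRM for endpoints assessed at multiple visits, with T2DM, treatment, visit, treatment-by-visit and baseline value, and an unstructured covariance. Protocol 13.2.2 likewise limits the MMRM to endpoints measured often enough after baseline.

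**Digital-pathology paragraph.** SAP 9.2 then says that the three continuous variables "will be summarized descriptively with change from baseline being analyzed using MMRM methods". Their stage or grade versions get an ANCOVA with treatment, T2DM, F2/F3 and baseline value. Stage shifts (decrease, no change, increase) are presented in addition: "The shifts will be compared between treatment groups using a CMH-row mean scores test". No strata are named. SAP 7.1 says that selected tests are stratified and leaves the details to later sections.

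**Direction.** SAP 7.4 lists endpoint 18 as one-sided, lower being better. The general ANCOVA and MMRM text in SAP 9.2 mentions two-sided p-values only. SAP 7.3 says that one-sided endpoints will also have two-sided p-values.

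**The concern.** The digital-pathology paragraph departs from the SAP's own rule a few lines earlier and from the protocol. Three things follow.

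- The continuous and staged versions of one reading are adjusted differently. The randomisation factor F2/F3 is in the protocol's ANCOVA for this endpoint and in the SAP's stage/grade ANCOVA, but not in the model for the continuous values. SAP Section 11 declares the removal of region only.
- A model with a visit term makes visit assignment matter, and SAP 7.10 does not clearly place early-termination biopsies at Week 52.
- The programmer must decide whether the shift test is stratified and how its one-sided p-value is formed. These choices should be fixed before unblinding.

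At stake are the consistency and a little of the precision of one secondary endpoint. The validity of the trial's main result is not affected.

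**Working it through.** **1. The plan's own figure.** The documents give no size or precision figure for endpoint 18. The only sizing is for the primary endpoint (40% vs 20%, one-sided 0.05, 80% power, 2:1). The unpooled normal approximation gives placebo n = (1.645 + 0.842)² × (0.2×0.8 + 0.4×0.6/2) / 0.2² = 6.18 × 0.28 / 0.04 = 43.3, so 44 placebo and 88 active, 132 in all. 132/0.815 = 162, as stated. I use 132 (88:44) below only as a realistic number of evaluable subjects.

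**2. Values per subject.** One set of biopsies, taken at Baseline and Week 52 (or at early termination after at least 42 weeks), gives one post-baseline value. That is the ANCOVA case under SAP 9.2.

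**3. What the MMRM becomes with one visit level.** Visit equals the intercept, treatment-by-visit equals treatment, and the unstructured matrix is 1×1. On simulated data with n = 132, the over-parameterised design has 9 columns and rank 4, the same rank as the ANCOVA with T2DM and baseline value. Residual df = 132 − 4 = 128.

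| Model | Difference | SE | df |
|---|---|---|---|
| MMRM, one visit | −0.4697 | 0.1020 | 128 |
| ANCOVA (T2DM, baseline) | −0.4697 | 0.1020 | 128 |

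The fits are identical.

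**4. Adjustment sets.**

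| Source | T2DM | F2/F3 | Region | Baseline value |
|---|---|---|---|---|
| Protocol 13.2.2 ANCOVA | yes | yes | yes | yes |
| SAP 9.2 MMRM, continuous variables | yes | no | no | yes |
| SAP 9.2 ANCOVA, stage/grade variables | yes | yes | no | yes |

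Only the loss of region is declared in SAP Section 11.

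**5. Early termination.** SAP 7.10 analyses such data at the closest scheduled visit. Scheduled visits include Weeks 39 and 52, with midpoint (39 + 52)/2 = 45.5. A biopsy between Weeks 42 and 45.5 is therefore closest to Week 39, where no biopsy exists to displace it. There would then be two visit levels but still one value per subject, and those subjects would leave the Week 52 contrast. The Week 39/52 covariance never enters the likelihood. With 12 of 132 simulated subjects placed at Week 39 and both variances held at 0.36, the REML log-likelihood is 3.0985 at covariances of −0.2, 0 and +0.2. The parameter cannot be estimated. The fallback structures (spatial power, compound symmetry) have the same problem, because their correlation parameter also needs two values from some subjects.

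**6. Shift test.** The simulation had 132 subjects at 2:1, 50% F3, 60% T2DM, scores −1/0/+1, one-sided 5% and 4,000 runs per line. The prevalences, stratum effects and treatment effect are assumptions. The stratified test uses F2/F3 × T2DM.

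| Assumed stratum effect | Type I error, unstratified | Power, unstratified | Power, stratified | Loss (points) |
|---|---|---|---|---|
| none | 5.0% | 69.9% | 70.2% | 0.3 |
| weak | 5.2% | 69.4% | 69.9% | 0.5 |
| moderate | 4.4% | 66.4% | 68.4% | 2.0 |
| strong | 3.3% | 61.7% | 68.4% | 6.7 |

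The Monte Carlo standard error at 5% is √(0.05×0.95/4000) = 0.3 points, so 5.2% is compatible with the nominal level.

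A second scenario used 20,000 trials and stratified by F2/F3 only. Assumed shifts (down/same/up) were 20/50/30% in F2 and 50/40/10% in F3 on control, and 35/45/20% and 65/30/5% on active. Unstratified size was 3.9% and power 52.6%; stratified, 5.0% and 56.4%.

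**The case against.** The strongest reply is that little changes in practice. The collapsed MMRM is exactly the ANCOVA that SAP 9.2 prescribes for single-time endpoints, so the label alone does not alter the estimate. The model already adjusts for the baseline value of the same measurement, so adding F2/F3 is a choice of adjustment and does not repair an invalid analysis. Biopsies are scheduled only at screening and Week 52, and SAP 7.11 accepts histology on or after Week 42 for the responder endpoints, so a sensible programmer would place an early-termination biopsy at Week 52. The shift test is additional to an ANCOVA of stage/grade change that adjusts for T2DM and F2/F3. In the second scenario, a linear model on the same three-level score with treatment and F2/F3 had power 56.4% and size 4.9%, so an adjusted analysis of that kind recovers the whole loss there. Endpoint 18 is also one of many secondary endpoints without multiplicity control.

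Most of this stands, and it sets the severity. It does not remove the contradiction in the text, the undeclared loss of F2/F3, or the gap in SAP 7.10, since SAP 7.11 covers responder status and not the visit assigned to continuous values.

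A reader might infer more than the documents support:

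- That the model cannot be fitted, or is wrong for the data. With one visit level it fits and equals ANCOVA; an estimation problem arises only under the literal reading of SAP 7.10.
- That subjects without a biopsy are lost through the choice of model. No section claims missing-at-random handling for this endpoint, and the ANCOVA would not recover them either.
- That the row-mean-scores test has no direction. With two arms it has 1 df, and the sign of the mean-score difference supplies the direction.
- That F2/F3 dominates the shift. The documents do not say so, and F2/F3 is the NASH CRN stage, not the baseline qFibrosis stage whose shift is tested.

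**Conclusion.** The point holds as a minor inconsistency. SAP 9.2 gives an MMRM to three variables with one post-baseline value, against its own rule and Protocol 13.2.2. With Week 52 as the only visit, the result is a valid ANCOVA with T2DM and baseline value. The real differences are the undeclared omission of F2/F3, whose effect on precision cannot be sized from the documents, and an ambiguous visit assignment for early-termination biopsies between about Weeks 42 and 45.5. How many subjects that would involve is unknown and may be none.

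The unstratified shift test is valid. It can be conservative (type I error 3.3% to 5.2% in the simulations) and loses roughly 0 to 7 points of power. That range rests on assumed stratum effects and prevalences; if the strata are not prognostic, there is no material loss.

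**What to change.** In SAP 9.2:

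1. For continuous qFibrosis, qSteatosis and steatosis-corrected qFibrosis, replace the MMRM with an ANCOVA of change at Week 52 with treatment, T2DM, F2/F3 and baseline value. This is the model already given for the stage/grade variables.
2. State that, for all digital-pathology variables, an early-termination biopsy obtained on or after Week 42 is analysed as Week 52, whatever SAP 7.10 would otherwise imply. This matches the Week 42 limit in SAP 7.11.
3. Stratify the CMH row-mean-scores shift test by T2DM and F2/F3, and keep the three-category scores.
4. For endpoint 18, report the signed one-sided p-value (lower is better) next to the two-sided one, as SAP 7.3 and 7.4 require.

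The cost is SAP wording and minor programming before unblinding. All variables are already collected, and the sample size does not change.

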9.3. Exploratory Efficacy Endpoints Analyses

Analysis of exploratory endpoints will be based on the ITT and mITT populations. Exploratory efficacy endpoints expressed as a proportion will be analyzed using the methods described for the primary efficacy endpoint. While the endpoints expressed as change from baseline and percent change from baseline will be analyzed using descriptive summary statistics and with ANCOVA or MMRM at a later date, if warranted.

9.4. Pharmacokinetics (PK)

All PK analyses will be described in a separate PK analysis plan. PK concentration data will be listed.

10. SAFETY

Safety will be evaluated based on data collected for adverse events, vital signs, physical examinations, electrocardiogram (ECG), ophthalmologic examinations, and laboratory data. No formal statistical testing will be conducted for the safety analyses. Descriptive statistics will be used to evaluate safety data in this study. Summaries will be presented by treatment group.

All safety analysis reporting will be based on the Safety population. All safety data will be listed by treatment group and subject.

10.1. Adverse Events

An AE is any untoward medical occurrence in a subject or clinical investigation subject administered a pharmaceutical product, and which does not necessarily have to have a causal relationship with this treatment. An AE can therefore be any unfavorable and unintended sign (including abnormal laboratory findings), symptom, or disease temporally associated with the use of an investigational product, whether related to the investigational product or not.

An unexpected AE is any event for which the nature or severity is not consistent with the information in the current Investigator's Brochure.

Any abnormal clinical or laboratory finding considered by the Investigator to be clinically significant is to be recorded in the eCRF as part of the subject's medical history if occurring prior to the start of study drug administration and as an AE if occurring after the start of study drug administration at baseline, where the finding represents a change from baseline.

A treatment emergent AE (TEAE) is defined as any AE occurring after the first dose of study treatment. All summaries of AEs will be based on TEAEs. All AEs recorded on the eCRF, whether treatment emergent or not, will be presented in the data listing. Non-TEAEs will be flagged in the listings.

Adverse Events will be coded using MedDRA version 24.0 or higher for reporting by SOC and PT. Summaries of TEAEs by SOC and PT will be presented in descending order of overall incidence. TEAEs will also be summarized by maximum intensity as classified according to the National Cancer Institute (NCI) Common Terminology Criteria for Adverse Events (CTCAE), Version 5.0 (or higher). If the AE is not included in the NCI CTCAE, then the Investigator is to determine the severity of the AE according to the criteria provided in the study protocol.

The causal relationship of each AE to study drug will be determined by the Investigator according to best medical judgment as definitely related, probably related, possibly related, unlikely related, or unrelated. If the relationship between the AE and study drug is determined to

be “possible”, “probable”, or “definite”, the event will be considered treatment-related for the safety analyses.

Missing severity assessments will be listed as missing information. Missing relationship assessments will also be listed as missing information. All AE summaries will be produced using the safety population and displayed by treatment group and overall.

An overview of TEAEs will be produced, including counts and percentages of subjects with any incidences of: TEAEs, TEAEs related to study treatment, serious adverse events (SAEs), TEAEs leading to study drug discontinuation, TEAEs with CTCAE grade 3 or higher, and fatal SAEs. The number of AEs will also be included in the summary.

In addition to the overview of TEAEs, the following summaries of AEs will be provided for the safety population by treatment group and overall:

- TEAEs by SOC and PT
- TEAEs related to study treatment by SOC and PT
- CTCAE Grade 3 or higher TEAEs by SOC and PT
- CTCAE Grade 3 or higher TEAEs related to study treatment by SOC and PT
- SAEs by SOC and PT
- TEAEs leading to treatment discontinuation by SOC and PT
- Skin and subcutaneous tissue disorders TEAEs by PT
- Eye disorder TEAEs by PT

Summaries of TEAEs by SOC, PT, and maximum severity as well as TEAEs by SOC, PT, and maximum relationship to study treatment will also be prepared.

Skin and subcutaneous tissue disorders and eye disorder TEAE summaries will also be performed for the mITT population.

A comprehensive listing of all AEs will be provided in a by-subject data listing. In addition, the following listings will be provided:

- TEAEs related to study treatment
- SAEs
- TEAEs leading to treatment discontinuation; and
- Fatal AEs.

